4.3.2 Prior and Concomitant Medication

Prior or concomitant medication taken by or administered to a participant will be recorded in the case report form. The prior and concomitant medications will be coded using an internal validated medication dictionary, GSK Drug.

Prior medications are defined as those which stopped before the first administration of study product start date. If the stop date is unknown or incomplete and medication cannot be considered as stopped prior to first administration then the medication will be considered as concomitant medication.

Concomitant medications are defined as the medications ongoing on or after first study product start date.

Unknown dates will not be imputed, however if the start date is unknown, then it will be assumed to concomitant medication, unless the partial start date or stop date indicates differently.

Prior and concomitant medications/non-drug therapies will be listed by participant, with preferred term, indication, dose, dose form, frequency, route, start date, end date or ongoing and start day relative to first dose of study product ([Listing 16.2.5.2](#) and [Listing 16.2.5.3](#)).

4.4 Analysis of Efficacy

4.4.1 Primary Efficacy Endpoint

4.4.1.1 Primary Efficacy Endpoint Definition

The primary efficacy variable of the study is the number of ill days over a period of nine months.

The definition of number of illness days is following –

Number of illness days: Number of days a subject is ill because of GI and/or respiratory illnesses as diagnosed by study physician, as per the criteria defined, over the intervention duration. This corresponds to total number of days (symptomatic or asymptomatic) in an episode of illness. Each episode is defined as each incidence of illness followed by at least 3 symptom free days.

In an episode if the first occurrence is due to GI illness and second occurrence is due to respiratory illness with less than 3 symptom free days then the overall episode due to GI and/or respiratory will be counted as one and separately it will be one each for GI and respiratory.

The asymptomatic days (or symptom free) days will be calculated programmatically based on the date mentioned on the Diagnosis Form in the following way –

Asymptomatic day = (Second occurrence start date - First occurrence end date) - 1

If asymptomatic day is less than 3 days then two occurrences of illnesses will be calculated and considered as single episode.

Else if asymptomatic days are greater than or equal to 3 days then two occurrences of illnesses will be calculated and considered as different episodes.

Descriptive statistics (n, mean, SD, SE, median, minimum and maximum) by product group will be provided ([Table 14.2.2.1](#)). Number of ill days due to GI and/or respiratory illnesses will be listed for each subject ([Listing 16.2.6.18](#)).

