6.11.3. Clinical Evaluation Tools

A. Parent/LAR reported Symptom Checklist

At the beginning of the study, parents/LARs will be provided with blank ‘symptom checklist’ forms. The symptom checklist to be used by the parents/LARs has been appended (Appendix 3). When a symptom is observed in the participant during the intervention period, the parents will be required to fill the symptom checklist as trained by study staff. The severity/intensity of severity assessment of the symptoms e.g. sore throat, dry cough, wet cough, runny nose, stuffy/blocked nose and sneezing will be made by parents/LARs as per the following criteria:

- Mild – Easily tolerated, causing minimal discomfort and not interfering with normal everyday activities.
- Moderate – Sufficiently discomforting to interfere with normal everyday activities.
- Severe – Any event that prevents normal everyday activities.

Parents/LARs will be trained by study staff to assess the symptoms based on above criteria. For the assessment of other symptoms e.g. diarrhea/loose stools, vomiting and fever, the criteria are already mentioned in the symptom checklist which are in

	Document Name	Clinical Study Protocol 204477		
	Type	Version	Document Identifier	Effective Date
	eldo_clinical_doc	5.0; Most-Recent; Effective; CURRENT	090032d580daa95e	10-Oct-2017 06:16:49
	Reason For Issue	Auto Issue		

line with assessment done as per CTCAE 2010. Parents/LARs will also be provided with digital thermometers to check temperature in case if fever is observed.

In cases where parents/LARs do not observe any symptoms in the participant, they will be asked to mark the relevant ('No') box mentioned for each symptom for each day in the symptom checklist. The symptom checklist will be handed to study physician on weekly basis for review by physician. The physician will then evaluate the symptoms, if any, to determine diagnosis.

Those requiring hospitalisation or specialised care will be referred to the secondary or tertiary care hospital, as deemed necessary by the study physician. The determined diagnosis will be captured in the CRF, and the severity will be graded based on the criterion indicated in Appendix 5.

B. Diagnosis Form

Diagnosis form (DF) will be used to note the diagnosis, severity and school absenteeism due to GI and respiratory illnesses only, as defined in the study protocol. DF will also be used to capture start and end date of all occurrences of GI and respiratory illnesses in the week.

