6.12. Study Physician Weekly Review

To ensure that no case is missed, a weekly review (SPWR) will be scheduled by the study physician to check symptom checklist from all participants.

 GlaxoSmithKline	Document Name	Clinical Study Protocol 204477		
	Type	Version	Document Identifier	Effective Date
	eldo_clinical_doc	5.0; Most-Recent; Effective; CURRENT	090032d580daa95e	10-Oct-2017 06:16:49
	Reason For Issue	Auto Issue		

SPWR will initiate 1 week (+up to 2 days) post first dietary counselling visit of the participant and will continue on a weekly basis (+ up to 2 days) until end of study visit. ~~At least one weekly review with the study physician will occur after product administration stops~~ **LAST SPWR WILL BE CONDUCTED ON END OF STUDY VISIT DAY, EVEN IF SYMPTOMS ARE ASSESSED FOR LESS THAN A WEEK IN SYMPTOM CHECKLIST FORM.**

In case the SPWR of a participant is not conducted due to reasons such as absenteeism, long holidays etc for a week, then every attempt will be made to contact and collect symptom checklist from participant/parents/LARs, either telephonically or visiting them at home. If any participant is not accessible for consecutive 4 weeks, he/she will be considered as lost to follow up.

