12.5. Appendix 5 - Diagnosis Form (DF)

Screening Number _____ **Week: From** ___/___/___
To ___/___/___

1. Was a parent/LAR symptom checklist received for this week? Yes/No
2. Did the subject inform the study physician directly of any Symptoms? Yes/No
3. If any symptoms were confirmed, was a diagnosis for GI and respiratory illnesses provided by the study physician? Yes/No/Not applicable

Note:

- a) If applicable, fill out the following diagnosis chart
- b) No. of ill days will be calculated programmatically for GI and respiratory illnesses reported in the study.
- c) School absenteeism in the DF will be marked for absenteeism due to GI and respiratory illnesses only.
- d) Number of episodes of illness for a particular week will be determined programmatically.
- e) Parents/LAR will also be asked to report to the study physician/study staff any other symptoms observed in participants but are not listed parent/LAR symptom checklist and will be entered in the AE forms.

GlaxoSmithKline

Document Name	Clinical Study Protocol 204477		
Type	Version	Document Identifier	Effective Date
eldo_clinical_doc	5.0; Most-Recent; Effective; CURRENT	090032d580daa95e	10-Oct-2017 06:16:49
Reason For Issue	Auto Issue		

Diagnosis Occurrences in this week	GI Illnesses (Yes  No )		Respiratory Illnesses (Yes  No )
	Diarrhea 	Vomiting 	
First Occurrence			
AE Report Number (from paper AE form)			
Start Date			
End Date			
Severity	 Mild  Moderate  Severe	 Mild  Moderate  Severe	 Mild  Moderate  Severe
School absenteeism (No. of days in this week)			
AE Number (from eCRF)			
Second Occurrence			
AE Report Number (from paper AE form)			
Start Date			
End Date			
Severity	 Mild  Moderate  Severe	 Mild  Moderate  Severe	 Mild  Moderate  Severe
School absenteeism ¹ (No. of days in this week)			
AE Number (from eCRF)			
Third Occurrence			
AE Report Number (from paper AE form)			
Start Date			
End Date			

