4.1.3 Analysis Populations

Six analysis populations are defined.

| Population | Definition / Criteria | Analyses Evaluated |
|--------------------------|---|---|
| All Screened Subjects | 
 All participants who enter the study and sign the informed consent form. This population includes screen failures as well. | 
 Disposition, AE listing |
| Enrolled Population | 
 All participants who attended baseline visit will be considered in enrolled population. | 
 Protocol deviations, AE, efficacy, demographic characteristic, disposition and medical history listings |
| Safety | 
 Comprise of all participants who received at least one dose of study product (i.e. either only dietary counselling or both supplement and dietary counselling) during the study. This population will be based on the product to which the participant was planned to receive. | 
 Safety |
| Intent-To-Treat (ITT) | 
 All participants in the safety population with any post-treatment assessment (SPWR is considered as post-treatment assessment) will be included in Intent-to-treat (ITT) population. This population will be based on the product to which the participant was planned to receive. | 
 Efficacy |
| Modified Intent-To-Treat | 
 All participants in the ITT population who have completed entire study of 9 months | 
 Primary, Secondary |

| Population | Definition / Criteria | Analyses Evaluated |
|--------------|--|--|
| (mITT) | 
(i.e., attended up to end study visit) will be included in modified intent-to-treat (mITT) population.
 
 This population will be based on the product to which the participant was planned to receive. | Exploratory Efficacy |

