4.4.2 Secondary Efficacy Variables

The analysis of secondary efficacy variables will be on the mITT population.

The secondary efficacy variables are:

- **Frequency of GI and Respiratory illness**

Frequency of GI and respiratory illnesses defined as total number of illness episodes of GI and/or respiratory illnesses, divided by duration of intervention in month, where each episode is defined as each incidence of illness followed by at least 3 symptom free days will be summarized in a table for the product groups (Table 14.2.3.1).

The frequency of GI and respiratory illnesses will be calculated as following –

Frequency (per month) = No of episodes X 30/ Number of days between first (BV) and last visit

Frequency of GI and respiratory illnesses will be analysed together using analysis of covariance (ANCOVA) model. The model will include cluster (school) as a random effect; fixed effects for product group and gender; and baseline IDDS as a covariate. Adjusted means, 95% confidence intervals, intraclass correlation, within product group p-values for each product group, product group difference, 95% confidence interval of the difference and the between-product group p-values based on the statistical model described above will also be presented (Table 14.2.3.2).

The assumptions of normality and homogeneity of variance will be investigated and violation of these assumptions may be overcome using suitable transformation or by performing sensitivity analysis or by appropriate non-parametric tests (e.g., Van Elteren, rank ANCOVA).

- **Analysis on Severity of GI and Respiratory illness:**

Frequency and percentages of severity episodes of GI and respiratory illnesses will be summarized in a table together and also separately (Table 14.2.4.1). If an episode comprises of occurrences of different severities, then the highest severity will be considered as the overall severity. Severity grades will be displayed in the tables for the GI and respiratory illness as mentioned in the Appendix 5 of the Protocol version 5.0.

Frequencies of severity (Mild, moderate, or severe) episode between product groups will be compared using Chi-Square test (if frequencies are greater than 5%). If frequencies are $\leq 5\%$ in any product group, then these will be compared using Fisher's exact test between product groups (Table 14.2.4.1).

- **Analysis of School absenteeism due to GI and Respiratory illness:**

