4.4.3 Handling of Missing Values/Censoring/Discontinuations

Missing endpoints data will not be imputed, only subjects that completed the study are included on the mITT population.

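### Weeks that no source recovers add zero ill days to the primary count, and neither the primary ANCOVA nor the MMRM allows for time actually observed

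*SAP*

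**What the plan says.** **Endpoint.** SAP 4.4.1.1 states: "The primary efficacy variable of the study is the number of ill days over a period of nine months". A day counts if it falls under the "Number of days a subject is ill because of GI and/or respiratory illnesses as diagnosed by study physician". Asymptomatic days inside an episode count as ill, and a gap of three or more asymptomatic days ends the episode.

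**Source.** Protocol 6.11.3: "DF will also be used to capture start and end date of all occurrences of GI and respiratory illnesses in the week". Ill days and episodes are then derived by program from that form.

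**Missed reviews.** Protocol 6.12 tells staff to try to obtain the checklist by telephone or home visit. It then says: "If any participant is not accessible for consecutive 4 weeks, he/she will be considered as lost to follow up". Shorter gaps may recur without ending follow-up.

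**Primary set and missing data.** SAP 4.1.3 admits ITT children who completed nine months: "i.e., attended up to end study visit) will be included in modified intent-to-treat (mITT) population". No minimum of observed weeks is set. SAP 4.4.3 adds: "Missing endpoints data will not be imputed, only subjects that completed the study are included on the mITT population". Protocol 9.2.5 also rules out imputation. The MMRM table shell in SAP Attachment 1 nevertheless mentions imputed data, without a method.

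**Models.** The ANCOVA (SAP 4.4.1.2) has school, product group, gender and baseline IDDS. The MMRM (SAP 4.4.1.3) adds visit and its interaction with group. Neither has an offset, rate or observed-time covariate. Episode frequency (SAP 4.4.2) is divided by the "Number of days between first (BV) and last visit", which is calendar time.

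**What is collected.** Item 1 of the Diagnosis Form (Protocol Appendix 5) asks: "Was a parent/LAR symptom checklist received for this week? Yes/No". No planned table or model uses the answer.

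**The concern.** A sum of recorded illness dates cannot tell a healthy week from an unseen one. If unseen weeks were equally common in both arms, the difference would only shrink slightly. If they differ by arm, the primary comparison partly measures how completely weeks were reported. This is separate from dropout, because it happens among children who attended the last visit.

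An imbalance is plausible. The trial is open label. Test children have two supervised doses on each school day (Protocol 5.3), random home visits (5.5) and sachet accounting (5.10.1); controls have no product contact. With two schools per arm (SAP 3.3), poor checklist return at one school moves its arm's mean directly, and a random school effect cannot separate that from treatment. No planned output would show whether an imbalance occurred.

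**Working it through.** **1. The plan's sample size reproduces.** Inputs (Protocol 9.1, SAP 1.4): means 7.0 and 6.3, SDs 2.65 and 2.51, two-sided 5%, 80% power, design effect 1.5, 30% dropout.
- Pooled SD = sqrt((2.65² + 2.51²)/2) = 2.581.
- The normal approximation gives 214 per arm. The exact t-test needs 215 (power 0.801 at 215, 0.799 at 214).
- 215 × 1.5 = 322.5, rounded up to 323. Then 323/0.7 gives 462 per arm, 924 in total.

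**2. What one unseen week is worth.** Nine months is about 274 days, or 39 weeks.
- 7/39 = 0.18 ill day per week; 0.18/0.7 = 26% of the planned effect.
- Two weeks: 0.36 day (51%). Weeks equal to the whole effect: 0.7/(7/39) = 3.9.
- If only one of an arm's two schools, taken as equal in size, misses the extra week, the arm mean moves by 0.09 day (13%).

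This assumes that illness in unseen weeks occurs at the average rate. If children miss review because they are ill, the undercount is larger.

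**3. Direction.**
- Extra unseen weeks in the control arm, true 10% reduction: the observed difference is 7 × (1 − d/39) − 6.3, which is 0.52 for d = 1, 0.34 for d = 2 and 0.00 for d = 3.9.
- Extra unseen weeks in the test arm, no true effect: a spurious difference of 0.18, 0.36 and 0.70 day favouring the product.
- Equal missingness, true 10% reduction: 0.7 × 37/39 = 0.66 with 2 weeks missed in each arm, and 0.7 × 35/39 = 0.63 with 4.

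**4. In the sample-size frame only.** With SE = sqrt((m_C + m_T)/323 × 1.5), power falls from 0.80 to 0.56 and 0.29 for 1 and 2 extra control weeks. The false-positive rate rises from 0.05 to 0.11 and 0.30 for 1 and 2 extra test weeks. Equal missingness of 2 or 4 weeks leaves power at 0.78 or 0.76.

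**5. Gap formula.** Suppose one occurrence ends on day 14, days 15 to 21 are unseen, and the next occurrence starts on day 22. Asymptomatic days = (22 − 14) − 1 = 7. As 7 is at least 3, there are two episodes and none of the 7 days counts. Had the child been ill throughout, the truth would be one episode and 7 more ill days.

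**6. Does observed time repair it?** In a Poisson simulation (4,000 runs, 215 effective children per arm, 2 missed weeks assumed in each arm as a base, missingness unrelated to illness), an observed-weeks offset gave type I error of 0.052 to 0.053 with 2 to 3.9 extra test-arm weeks. Power for a true 10% reduction was 0.78 and 0.76 with 2 and 3.9 extra control-arm weeks; the raw count rejected in 0.26 and 0.06 of runs.

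**7. The denominator must not depend on illness.** Assume that 10% of weeks lack a checklist, the physician catches half of the illness in them, and 5% to 18% of weeks contain illness.
- Raw count: 0.90 + 0.05 = 0.95 of the truth.
- Counting a week as observed whenever a form was completed for illness: 0.95/(0.90 + 0.0025 to 0.009) = 1.05 to 1.045, an error of similar size in the other direction.
- Restricting numerator and denominator to weeks ascertained regardless of illness: 0.90/0.90 = 1.00.

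**The case against.** The plan is not silent, and several safeguards narrow the problem.

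- **A missing checklist is not an unseen week.** Protocol 6.12 requires recovery attempts. A physician is at school on every school day with no distinction by arm (6.12.2). The form also draws on external records and direct reports (6.11.3). A reader might infer that every week without a checklist scores zero; it does so only when all these routes fail. They are weaker for illness at home, in holidays or during absence.
- **A per-protocol analysis exists.** SAP 4.1.3 treats the weekly review as a post-treatment assessment and requires all such assessments for PP, so a child with a missed review should fall out. PP is run on the primary variable if it excludes more than 5% of mITT. SAP 3.4 adds case-by-case review of schedule deviations. This stands, but PP is conditional, supportive and selective, and it leaves the mITT result as it was.
- **Direction.** A reader might infer that the design favours the product. The documented contact difference points the other way: fuller capture in test schools raises test-arm ill days and works against the required decrease (Protocol 9.2.3). No passage supports more unseen weeks in the test arm.
- **Size.** No missed-week rate is given, and matching the planned effect needs an average arm difference of 3.9 fully unrecovered weeks per child. The error rates in step 4 use a simple test with design effect 1.5. They should not be read as properties of the SAP's random-effect model with four schools.

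**Conclusion.** The point holds in a limited form and should be fixed. The documents never write that an unrecovered week is zero, but it follows from summing form dates, not imputing, defining completion by the last visit, and having no observed-time term in the ANCOVA or MMRM. The safeguards reduce the number of such weeks without removing them from the primary mITT result.

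The shift is about 0.18 day per child for each extra unrecovered week in one arm, 26% of the planned effect. It rests on 7 ill days spread evenly over 39 weeks and on a difference between arms or schools in unrecovered weeks. That difference is an assumption, illustrated here from 1 to 3.9 weeks. The likelier consequence is a masked benefit. A false positive is arithmetically possible, but nothing in the documents makes it the expected outcome.

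**What to change.** Amend the SAP before database lock:

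1. In 4.4.1.1, define an observed week as one in which symptom status was ascertained whether or not the child was ill: checklist received or recovered (Diagnosis Form item 1 answered yes), or a scheduled weekly review actually conducted. A form's mere existence, or a visit prompted by illness, should not qualify.
2. Tabulate unobserved weeks by arm and by school.
3. Pre-specify an analysis of ill days per observed time, with observed days as denominator or offset and with numerator and denominator restricted to the same observed weeks. Report it beside the raw count.
4. Apply the same denominator to episode frequency as a sensitivity analysis.
5. In the gap formula, do not treat unobserved days as symptom-free. Report results with episodes that span an unobserved gap both merged and split.
6. Reconcile the MMRM table note on imputed data with SAP 4.4.3 and Protocol 9.2.5.

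The cost is SAP wording and programming. Item 1 is already collected weekly; the team should confirm that the database also shows which reviews took place. Children with few observed weeks will have noisier rates, and illness known only from a direct report in an unobserved week is left out of the rate analysis, which is why the raw count stays beside it. The rate analysis also assumes that illness in unobserved weeks resembles that in observed ones.

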4.4.1.2 Statistical Hypothesis, Model, and Method of Analysis

For the primary variable, primary analysis will be performed on participants on the mITT population.

The null hypothesis of interest is:

H0: There is no difference between the numbers of illness days for the product groups.

The alternative hypothesis of interest is:

H1: There is a difference in between the numbers of illness days for the product groups.

The number of ill days will be analysed using the analysis of variance (ANCOVA) model. The ANCOVA will have cluster (school) as a random effect, product group and gender as fixed effects and baseline IDDS as a covariate.

Adjusted means, 95% confidence intervals (CI), within product group p-values for each product group, product group difference, intracluster correlation, 95% confidence interval of the difference and the between-product group p-values based on the statistical model described above will also be presented ([Table 14.2.2.2](#)).

All statistical tests of hypotheses will be two-sided and will employ a level of significance of $\alpha = 0.05$.

The simulated data used for the sample size calculations were based upon the assumption of a Poisson distribution per product group. However, on observation of these simulated data, it was considered that these Poisson distributions were not heavily skewed and, as a result, normal distributions may be assumed. Consequently, a normality assumption has been adopted for both the generation of sample size and the intended approach to the statistical analysis.

However, the assumptions of normality and homogeneity of variance will be investigated and violation of these assumptions may be overcome using suitable transformation (for example, log or square root or Poisson regression using Proc Genmod) or by performing appropriate non-parametric tests (e.g., Van Elteren, rank ANCOVA).

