- Sample collection for urinary Neopterin test & lactulose/mannitol test
- Sample collection for analysis of serum ferritin, sTfR, CRP, AGP, sIgA & nutritional biochemistry (for micronutrients vitamins A, B6, B12, C, D, E, folate, and of the trace elements selenium, zinc, copper, and iron)
- AE monitoring
- Study completion and medical sign-off

Type and Planned Number of Participants

Approximately 1300 participants will be screened in at least 4 clusters (with at least 2 clusters per study arm), to randomise approximately 924 participants to ensure 646 evaluable participants complete the entire study. This will ensure at least 323 evaluable participants per study arm.

Diagnosis and Main Criteria for Inclusion

Boys and girls, aged 7 to 10 years inclusive with HAZ of ≥ -3 to ≤ -1 will be invited to participate in this study.

Product Information

	Test Group	Control Group
Product Name	Fortified malt based food	No treatment
Product Formulation Code	CCI [REDACTED]	N/A
Dose	27 grams	N/A

 GlaxoSmithKline	Document Name	Clinical Study Protocol 204477		
	Type	Version	Document Identifier	Effective Date
	eldo_clinical_doc	5.0; Most-Recent; Effective; CURRENT	090032d580daa95e	10-Oct-2017 06:16:49
	Reason For Issue	Auto Issue		

Route of Administration	Oral	N/A
Dosing Instructions	27 grams powder made up in 150 mL lukewarm water administered twice daily	N/A

Statistical Methods

The primary efficacy variable of the study is the impact of treatments on the number of ill days. The number of ill days will be analysed using the analysis of variance (ANOVA). The ANOVA will have treatment, cluster (school) and gender as fixed effects. Comparisons will be made between test and control groups at 5% significance level. Ninety-five percent confidence intervals will also be constructed.

 GlaxoSmithKline	Document Name	Clinical Study Protocol 204477		
	Type	Version	Document Identifier	Effective Date
	eldo_clinical_doc	5.0; Most-Recent; Effective; CURRENT	090032d580daa95e	10-Oct-2017 06:16:49
	Reason For Issue	Auto Issue		

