6.1. Matched Pair Formation

Each school will be deemed as a cluster. Schools with following characteristics will be invited to participate in the study:

- ~~Located in peri-urban areas~~
- No government or sponsored micronutrient supplementation scheme running in past 6 months
- Mixed-gender education/co-education system of education
- No history of any outbreak or clustering of cases of infectious diseases in last month

Schools which agree to participate will be selected and will be subsequently matched for cluster size (in context to the number of children in 7-10 yrs age group), socioeconomic profiles of students, and type of school; government subsidised or private.

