6.3. Demographics

The following demographic parameters will be captured by the Investigator or designee and recorded on the CRF: year of birth, gender and race.

 GlaxoSmithKline	Document Name	Clinical Study Protocol 204477		
	Type	Version	Document Identifier	Effective Date
	eldo_clinical_doc	5.0; Most-Recent; Effective; CURRENT	090032d580daa95e	10-Oct-2017 06:16:49
	Reason For Issue	Auto Issue		

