4.2.1 Demographic Characteristics

Descriptive statistics (number of subjects [n], mean, and median, standard deviation [SD], minimum and maximum) for the continuous variables and frequency (n) and percentages (%) for categorical variables will be provided for demographic variables.

The continuous variable includes age (years), height (cm), weight (kg), BMI and HAZ and categorical variables include gender, race, and HAZ (for ranges:-3 to -2 and -2 to -1).

This data will be summarized descriptively for all participants in Safety (Table 14.1.4.1), ITT (Table 14.1.4.2), mITT (Table 14.1.4.3) and if required on the PP Population (Table 14.1.4.4). Demographic information will be listed (Listing 16.2.4.1) for enrolled population.

No formal statistical analysis will be performed for this data.

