4.4.1.3 Supportive Analyses

As a part of sensitivity analysis a Mixed Model Repeated Measure (MMRM) model will be used. MMRM model will be just an analysis including multiple visits with defined structure of correlation among visits. In this study unstructured covariance matrix will be used. The number of ill days will be analysed using model with cluster (school) as a random effect; product group, gender, and visit and (product group and visit) interaction as fixed effects and baseline IDDS as a covariate.

This will be conducted on the primary efficacy endpoints on the ITT population ([Table 14.2.2.2a](#)).

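### The models for ill days, episode frequency and absenteeism, and the supportive MMRM, adjust for gender and dietary diversity but omit age and baseline HAZ, which are known for every enrolled child and not balanced by the school matching

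*SAP*

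**What the plan says.** SAP 4.4.1.2 gives the primary model: "The ANCOVA will have cluster (school) as a random effect, product group and gender as fixed effects and baseline IDDS as a covariate". The supportive MMRM in SAP 4.4.1.3 also has school as a random effect, with "product group, gender, and visit and (product group and visit) interaction as fixed effects and baseline IDDS as a covariate". In SAP 4.4.2, episode frequency and school absenteeism each use school as a random effect, "fixed effects for product group and gender; and baseline IDDS as a covariate". Severity, in the same section, is compared by an unadjusted chi-square or Fisher's exact test.

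Both missing variables are available. The protocol synopsis defines eligibility as "Boys and girls, aged 7 to 10 years inclusive with HAZ of" -3 to -1, and SAP 4.2.1 tabulates both by arm: "The continuous variable includes age (years), height (cm), weight (kg), BMI and HAZ". Protocol 6.3 records "year of birth, gender and race", and Protocol 8.2 bars birth dates from the CRF.

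Protocol 6.1 says schools are "subsequently matched for cluster size (in context to the number of children in 7-10 yrs age group), socioeconomic profiles of students", and on type of school. SAP 3.3 fixes four schools, two per product group. SAP Section 5 justifies adding baseline IDDS on the ground that background diet is a confounder and that dietary diversity is associated with nutritional and socioeconomic status, which bear on children's immunity. It gives no reason for leaving out age or HAZ.

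**The concern.** The SAP adjusts for one marker of nutritional background and leaves out another that the trial measures on every child. The protocol's own introduction links malnutrition to susceptibility to infection, and diarrhoea to poorer growth. HAZ is the trial's measure of growth status, so the argument made for IDDS applies at least as directly to HAZ.

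The design gives little assurance that arms will match on child-level characteristics. Only four schools are allocated. The synopsis places consent and screening after the clusters are randomised, and Protocol 5.9.2 states that the study is open label. Gender is held to 40-60% within each group by a recruitment rule and is also in the model; age and HAZ have neither safeguard. Matching on the number of 7-10 year olds does not balance the age mix within that range. Matching on socioeconomic profile bears on HAZ only indirectly.

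The SAP will display any age or HAZ imbalance by arm but pre-specifies no response to it. At stake are some precision, some protection against confounding, and the avoidance of a covariate choice made after an imbalance has been seen.

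**Working it through.** **1. The plan's sample size reproduces.** From SAP 1.4: means 7.0 and 6.3, SDs 2.65 and 2.51, two-sided alpha 0.05, power 80%.
- Pooled SD = √((2.65² + 2.51²)/2) = 2.581.
- A two-sample t-test for a 0.7-day difference needs 215 per arm (214 by the normal approximation). The plan states 215.
- 215 × 1.5 = 322.5, so 323 per arm. 323/0.70 = 461.4, so 462 per arm and 924 in total. Both match the plan.

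The omitted covariates affect none of these figures.

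**2. How much of the contrast variance a child-level covariate can reduce.** Assume four equal schools with 323/2 = 161.5 evaluable children each.
- ICC implied by the design effect = (1.5 - 1)/(161.5 - 1) = 0.0031.
- Variance of the arm difference = 2 × 2.581² × 1.5/323 = 0.0619, so SE = 0.249.
- Child-level share = (1 - 0.0031)/1.5 = 0.66. The remaining third is between schools and is taken as unchanged.

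**3. Precision gain.** Let age and HAZ together explain R² of the child-level part (assumed; the documents give no value). The variance is then multiplied by 1 - 0.66 × R².

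| R² | SE | Nominal power | Power with 2 school-level df |
|---|---|---|---|
| 0 | 0.249 | 80.2% | 35% |
| 3% | 0.246 | 81.0% | 36% |
| 10% | 0.240 | 82.9% | 37% |

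Nominal power uses 644 df. The last column uses 4 schools - 2 arms = 2 df.

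**4. Shift if the arms differ.** Shift = slope × difference in arm means. Both inputs are assumed: slopes of 0.25-1.0 day per year of age or per HAZ unit, and gaps of 0.1-0.5.
- Smallest: 0.25 × 0.1 = 0.025 days, or 4% of 0.7.
- Middle: 0.5 × 0.25 = 0.125 days, or 18%.
- Largest: 1.0 × 0.5 = 0.50 days, or 71%.

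**5. How large a chance gap is plausible.** Assume ages uniform over a four-year span (SD = 4/√12 = 1.15), a HAZ SD of 0.5, and a school-level ICC for each covariate of 0-0.05. The SD of the arm difference is SD × √((1 + 160.5 × ICC)/161.5). This gives 0.09-0.27 years for age and 0.04-0.12 units for HAZ. A gap of 0.5 is therefore at least 1.8 such SDs for age (0.5/0.27) and about 4 for HAZ (0.5/0.12). The top of the range in step 4 is an extreme case under chance alone.

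**The case against.** The strongest reply is that this is a preference about covariates. Nothing in either document promises adjustment for age or HAZ, and no passage is contradicted. The SAP added one nutritional covariate and justified it. Eligibility already narrows both variables, socioeconomic matching gives some indirect control of HAZ, and any imbalance will be visible in the baseline tables. No passage reports an association of either variable with ill days within these ranges. All of this stands. It limits the size of the point but supplies no reason to omit two baseline values already collected.

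A reader might go further and infer that an age or HAZ gap passes directly into the treatment contrast as bias worth a large part of the 0.7-day target. The documents do not support that. The slopes and gaps are assumptions, and large shifts need the top of both ranges at once. Chance differences in school composition also form part of the between-school variance, which the random school effect carries into the standard error. They are imprecision rather than bias. What remains is possible systematic imbalance from open-label recruitment after allocation, which the random effect does not address. The documents show that opportunity but not that it occurred.

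A reader might also equate the precision gain with dozens of extra children. Applying R² to all 646 evaluable children ignores that only about two-thirds of the contrast variance is child-level.

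Finally, the change has a small limitation: with only year of birth on the CRF, age is coarse.

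**Conclusion.** The point holds as a modest, low-cost improvement. It is neither an arithmetic error nor a contradiction. Age and baseline HAZ are absent from the four models, known for every enrolled child, and outside the matching. The SAP's case for IDDS extends to HAZ; it does not cover age, where the argument rests on plausibility and on the weak balance that four schools provide.

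The benefit cannot be derived from the documents. At an assumed R² of 3-10% of child-level variance, nominal power rises by about 1-3 points. Under the assumed slopes and gaps, the shift avoided is 0.025-0.50 days, with the upper end unlikely by chance alone. Control of confounding, fixed in advance, is a better reason for the change than power.

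It would be wrong to infer that the added terms make the primary comparison secure. With two schools per arm and 2 school-level degrees of freedom, power stays near 35-37% with or without them.

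**What to change.** In SAP 4.4.1.2, 4.4.1.3 and the frequency and absenteeism parts of 4.4.2, add age (whole years, derived from year of birth) and baseline HAZ (continuous, from screening) as child-level covariates. Record the change and its rationale in SAP Section 5, and make it before data are reviewed by arm. If the sponsor prefers to keep the current primary model, name the extended model as a pre-specified sensitivity analysis.

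The cost is two model terms and the matching table footnotes, with no new data. Both variables vary within schools, so they use no school-level degrees of freedom. Both are fixed before product starts, so they cannot absorb a product effect. The severity comparison has no covariate model and would need a separate change.
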